 - Prevalence of each menopausal symptom including vasomotor symptoms, bone and joint symptoms, genitourinary symptoms, and psychosomatic symptoms will be calculated among patients with MHT.

- Within final study cohort, prevalence of menopausal hormone therapy by treatment class, age group, menopausal symptoms and the type of administration will be calculated for each year.
- Baseline characteristics including demographic characteristics, medical institution type, proxies of health status, comorbidities, and concomitant medications will be assessed on cohort entry date or within 365 days prior to cohort entry date. Type of administration will be assessed on index date. The baseline characteristics of patients with menopausal symptoms will be presented in frequency (proportion) for categorical variables and mean (standard deviation, SD) or median (interquartile ranges, IQR) for continuous variables.
- All outcome variables will be summarized descriptively through tables or graphical forms, including means, medians, ranges, and standard deviations of continuous variables, as well as frequency distributions of categorical variables.
- We will evaluate annual and quarterly time-series trends in the prevalence of MHT between 2012 and 2020 from 4 dimensions: 1) treatment class of MHT: ET (estrogen therapy), EPT (estrogen-progestin therapy), and tibolone. 2) age group: all, 40-44, 45-49, 50-54, and 55-59. 3) menopausal symptoms: vasomotor symptoms, bone and joint symptoms, genitourinary symptoms, and psychosomatic symptoms. 4) type of administration: systemic HT (oral), systemic HT (transdermal), and local HT (transvaginal).
- For treatment change pattern analysis, the treatment will be categorized and the proportional flows of patients switching the treatment classes will be demonstrated by Sankey diagram.
- Kaplan-Meier survival curves will be generated to calculate the time to non-persistence events including switch and discontinuation. Discontinuation will be defined as no subsequent prescriptions within 2 months of last prescription date.
- Treatment persistence is calculated by the average length of treatment of the drugs prescribed at the index date. Persistence rate at 3-, 6-, 9-, and 12-month were also calculated.
- Treatment adherence will be evaluated using medication possession ratio (MPR) calculated as the total number of days of medication supply divided by the number of days in the follow-up period.

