9.2. Setting

The study cohort will include patients aged 40-59 years who were firstly diagnosed with menopausal symptoms and initiated MHT between January 1, 2012 and December 31, 2019. Patients with menopausal symptoms will be defined as at least one inpatient or outpatient claim with any of the following diagnosis codes (Table 1), restricted to primary and secondary diagnosis. The cohort entry date will be defined as the date of first diagnosis of menopausal symptoms and the index date will be defined as the date of the first prescription for MHT.

The exclusion assessment window will be defined as the year before the index date. Patients meeting any of the following criteria will be excluded: 1) patients diagnosed with breast cancer (C50, D05), endometrial cancer (C54.1), or granulosa cell tumor (C56); 2) patients diagnosed with coronary heart disease (I20-I25, I51.6), stroke (I60-64), or VTE (I80.2, I80.3 I26); 3) Patients diagnosed with viral hepatitis (B16-B19), cirrhosis (K70.2-K70.4, K71.7, K72.0-K72.1, K72.9, K74.0-K74.6, K76.1, K76.6-K76.7, R18, I85.0, I85.9, I86.4, I86.8, I98.2-I98.3), and hepatic cancer (C22); 4) patients diagnosed with gallbladder disease (K80, K81, K82, K83, K85.1), gallbladder cancer (C23), extrahepatic bile duct cancer (C24) within 1 year prior to the index date. Baseline characteristics including demographic characteristics, and medical institution type will be assessed on cohort entry date and comorbidities, concomitant medications and proxies of health status will be assessed within 1 year prior to cohort entry date. Menopausal symptoms will be assessed within 90 days after cohort entry date. Type of administration will be assessed on index date. (Figure 1).

PFIZER CONFIDENTIAL

In the identified study cohort, we will examine treatment patterns, adherence, and persistence of MHT during the follow-up window, which will be defined from the index date (date of first prescription for MHT) to the end of the study period (December 31, 2020).

[figure not shown]
[figure not shown]

Figure 1. Study design scheme

[§] Menopausal symptoms: Vasomotor symptoms, Bone and joint symptoms

Figure 2. Study Flowchart

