9.2.1. Inclusion criteria

Patients must meet all of the following inclusion criteria to be eligible for inclusion in the study:

Using the HIRA database, which covers the entire Korean population of ≥ 50 million, we will include patients who meet all the following the inclusion criteria.

1. Patients aged 40-59 years at cohort entry date.
2. Patients who had at least one inpatient or outpatient diagnosis of menopausal symptoms (detailed below) between January 1, 2012 and December 31, 2019.

Table 1. Diagnosis codes for inclusion

KCD-8* code	Description
N95.1	Menopausal and female climacteric states
N95.2	Postmenopausal atrophic vaginitis
N95.3	States associated with artificial menopause
N95.8	Other specified menopausal and perimenopausal disorders
N95.9	Menopausal and perimenopausal disorder, unspecified
M80.0	Postmenopausal osteoporosis with pathological fracture
M81.0	Postmenopausal osteoporosis
M81.99	Osteoporosis, unspecified, site unspecified; Osteopenia

PFIZER CONFIDENTIAL

M85.99	Disorder of bone density and structure, unspecified, site unspecified; Osteopenia, mild; Osteopenia, moderate; Osteopenia, severe
--------	---

*KCD-8 (Korean standard classification of disease, 8th revision): Korean version of ICD-10 (International statistical classification of diseases and related health problems, 10th revision)

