- Over time since the index date (initiation of MHT), Kaplan-Meier survival curves will be generated to calculate the time to non-persistence events including switch and discontinuation. Discontinuation will be defined as no subsequent prescriptions within 2 months of last prescription date.
- Switching MHT for any other treatment classes. (i.e. Switch will be defined as when a patient initiating a ET is prescribed a tibolone or EPT)

6) Treatment persistence and adherence

- Treatment persistence is calculated by the average length of treatment of the drugs prescribed at the index date. Persistence rate at 3-, 6-, 9-, and 12-month will also be calculated.

- Treatment adherence will be evaluated using medication possession ratio (MPR), calculated as the total number of days of medication supply divided by the number of days in the follow-up period.

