9.3.4 Sensitivity analyses

We will conduct sensitivity analyses as follows:

1. Discontinuation will be defined as no subsequent prescriptions within 4 months of last prescription date.
2. Treatment patterns of medication use for MHT by index treatment classes with patients for 2 years of follow-up.

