We will examine annual time-series trends in the prevalence of use for MHT by menopausal symptoms: vasomotor symptoms, bone and joint symptoms, genitourinary symptoms, and psychosomatic symptoms. The time-series trend will be presented as the proportion of MHT use by each menopausal symptom, calculated as the number of patients with each menopausal symptom divided by the total number of patients prescribed with MHT.

We will examine annual time-series trends in the prevalence of use for MHT by the type of administration: systemic HT (oral), systemic HT (transdermal) and local HT (transvaginal). The time-series trend will be presented as the proportion of MHT use by each type of administration, calculated as the number of patients with MHT by each type of administration divided by the total number of patients prescribed with MHT.

Switching and discontinuation of MHT for any other MTH type will be shown by using Kaplan-Meier curve. Discontinuation will be defined as no subsequent prescriptions within 2 months of last prescription date. We will conduct a sensitivity analysis where discontinuation of MHT is defined as a 4-month period without any MHT.

Treatment persistence is calculated by the average length of treatment of the drugs that were prescribed at the index date. Treatment adherence will be shown by calculating MPR (medication possession ratio), calculated as a total number of days of supply of medication divided by the number of days of the follow-up period.

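### The medication possession ratio divides supply by all days to 31 December 2020, so it mixes adherence with duration of use and start date

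*Combined protocol and SAP*

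**What the plan says.** Section 9.3.2, item 6, defines MPR as "calculated as the total number of days of medication supply divided by the number of days in the follow-up period". The abstract (Section 4) and Section 9.7 repeat the rule: "medication possession ratio (MPR) calculated as the total number of days of medication supply divided by the number of days in the follow-up period" and "calculated as a total number of days of supply of medication divided by the number of days of the follow-up period".

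Section 9.2 says what follow-up means and applies it to adherence by name: "we will examine treatment patterns, adherence, and persistence of MHT during the follow-up window", and that window runs "from the index date (date of first prescription for MHT) to the end of the study period (December 31, 2020". The same section places the cohort's first prescriptions by date: "initiated MHT between January 1, 2012 and December 31, 2019".

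No text section ends the window at discontinuation, at a switch or at a fixed horizon. Figure 1 (study design scheme) is not reproduced in the copy available, so it cannot be checked. The only fixed length of follow-up mentioned is in Section 9.3.4, item 2: "Treatment patterns of medication use for MHT by index treatment classes with patients for 2 years of follow-up".

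**The concern.** The window closes on one calendar date for everyone, so its length is decided by when a woman started. Once she stops, each further day to the end of 2020 adds to the denominator and nothing to the numerator. Two women with the same prescriptions and the same stopping behaviour get different MPRs if they started in different years.

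Adherence is part of Objective 3 (Section 8), and MPR is its only stated measure. As written, MPR is the share of a window of about one to nine years that is covered by supply. It combines how regularly a woman took treatment, how long she stayed on it, and when she began. If MPR is compared between treatment classes whose mix changed over 2012 to 2019, start date alone could produce an apparent difference in adherence.

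**Working it through.** The documents give no MPR value, supply length or stopping rate, so there is no figure of the plan's own to reproduce. The inputs from the documents are the MPR formula (9.3.2, 9.7, abstract), the end of follow-up (9.2) and the range of start dates (9.2). Supply lengths, the share who stop, the coverage of those who continue, and an even spread of starts within each year are assumptions.

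**1. Denominator.** D = days from index date to 31 December 2020, counting both ends.
- Start 1 January 2012: D = 3,288
- Start 1 January 2019: D = 731
- Start 31 December 2019: D = 367

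3,288/367 = 8.96, so the denominator varies about nine-fold. Not counting both ends gives 3,287 and 366.

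**2. Everyone stops after S days of supply.** MPR = S/D, averaged over every start date in the year.

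| Start year | S = 90 | S = 180 | S = 365 |
|---|---|---|---|
| 2012 | 2.9% | 5.8% | 11.8% |
| 2016 | 5.5% | 11.0% | 22.3% |
| 2019 | 17.0% | 34.1% | 69.1% |

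The ratio of 2019 to 2012 is 69.1/11.8 = 5.9, and it is also 5.9 for 90 and 180 days, because S cancels. Other counting conventions change little for S = 365. Not counting both ends gives 11.8% and 69.3%; total supply over total follow-up gives 11.8% and 66.5%.

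**3. Some women continue.** A woman who continues at coverage c has supply c × D, so her MPR is c at any start date. With a fraction s stopping, the year's mean is s × (value in step 2) + (1 − s) × c. Take s = 0.5, c = 80% and S = 365:
- 2012: 0.5 × 11.8 + 0.5 × 80 = 45.9%
- 2019: 0.5 × 69.1 + 0.5 × 80 = 74.6%

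The ratio is 74.6/45.9 = 1.6. With s = 0 the values are equal and there is no distortion.

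**4. What a pooled figure would contain.** Give every woman the same 365 days of supply, let all stop, and spread starts evenly over 2012 to 2019. The pooled MPR has mean 27.4%, median 20.0% and interquartile range 14.3% to 33.3%. In this all-stop case supply is held constant, so the spread reflects start date only.

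**5. Ranking.** 180 days of supply from 1 January 2019 scores 180/731 = 24.6%. 730 days from 1 January 2012 scores 730/3,288 = 22.2%. The woman with about four times the supply scores lower.

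**6. Fixed window.** Over 365 days from index, 90, 180 and 365 days of supply give 90/365 = 24.7%, 180/365 = 49.3% and 100%, whatever the start date. The latest starter under Section 9.2 has 367 days, so every initiator completes the window.

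**7. Overlapping supply.** Cutting off supply at day 365 is not enough. 90-day prescriptions on days 1, 61, 121, 181 and 241 end on day 241 + 89 = 330, so all 5 × 90 = 450 supply days lie inside the window and MPR = 450/365 = 123%. Counting each calendar day once gives 330/365 = 90.4%; capping gives 100%.

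**The case against.** The strongest objection is to the size. The 5.9-fold gap supposes that every woman stops, and the protocol gives no persistence figure. This stands: the gap is 1.6-fold in the half-and-half case and vanishes if all continue at constant coverage. A reader might take 11.8% and 69.1% as the results to expect; the documents do not support that, and these values mark the all-stop end of a range.

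A second objection is that no planned table shows MPR by start year and no adherence threshold is set. This also stands. A reader might infer that the study will report a false rise in adherence over calendar time, but no such output is planned. The harm is limited to a pooled value that is hard to interpret, and to possible distortion in a comparison between classes.

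Third, the two-year sensitivity analysis may already supply a common window. Section 9.3.2 introduces all its outcomes under treatment patterns, which would include MPR; Section 8 lists adherence separately from treatment patterns. The wording does not settle it, and a sensitivity analysis leaves the primary MPR as it is.

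Fourth, Figure 1 might show a shorter window. That cannot be excluded, but the text of Section 9.2 would still need to agree with it.

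Finally, the study is descriptive (Section 9.5) and no test uses MPR. That limits the severity, but the descriptive figures are what such a study delivers.

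**Conclusion.** The MPR rule is wrong as written and should be fixed. Read with Section 9.2, it gives a denominator of 367 to 3,288 days set only by start date and counts all time after stopping as non-adherence. This part rests on the text and calendar arithmetic. The size rests on assumptions about stopping and coverage: a ratio of 2019 to 2012 starters of 5.9 if all stop, 1.6 if half stop and half continue at 80% coverage, and 1 if all continue at constant coverage.

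Two stronger readings do not hold. One is that the persistence results share the fault: the 3-, 6-, 9- and 12-month rates and the Kaplan-Meier curves do not use this denominator. The other is that women starting in 2020 enter with even shorter windows. Section 9.2.1 dates only the diagnosis ("Patients who had at least one inpatient or outpatient diagnosis of menopausal symptoms (detailed below) between January 1, 2012 and December 31, 2019"), but Section 9.2 limits initiation to the end of 2019.

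**What to change.** In Sections 9.3.2 and 9.7 and the abstract, define the primary MPR over a fixed 365 days from the index date, as days in that window covered by supply divided by 365. State how overlapping supply is handled: count each calendar day at most once, or cap MPR at 100%. The two can differ (90.4% against 100% in the early-refill example), so one must be named. State also whether supply after a switch of class counts.

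Keep the initiation limit of 31 December 2019 in the Section 9.2 index-date definition for the hormone-therapy analyses, so that every initiator has 365 days of data. Do not add it to Section 9.2.1 as an inclusion criterion, because Objective 2 also describes women without hormone therapy, and they would be excluded.

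The cost is a few sentences and minor programming, with no new data. The downside is that a fixed window removes the dependence on start date but still mixes adherence with duration within the year. Use beyond 12 months would be described only by the average length of treatment and the Kaplan-Meier curves.

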9.3.3 Baseline characteristics

We will identify the demographic and clinical characteristics of patients with menopausal hormone therapies.

- On cohort entry date
 - Age (40-44, 45-49, 50-54, 55-59)
 - Insurance type (national health insurance, medical aid)
 - Medical institution type (tertiary hospital, hospital, clinic)
- During 1-year prior to cohort entry date
 - CCI (Charlson Comorbidity Index)
 - No. of outpatient visits
 - No. of hospitalization
 - Comorbidities (diabetes mellitus, hypertension, dyslipidemia, cancer, anemia)

Table 5. Comorbidities

Comorbidities	KCD-8 code
Diabetes mellitus	E10-E14
Hypertension	I10-I15
Dyslipidemia	E78
Cancer	C00-C97 (except C22, C23, C24, C50, C54.1, C56)
Anemia	D50-D53, D55-D64

- Concomitant medications (bisphosphonate, denosumab, teriparatide, SERM, vitamin D, calcium)

Table 6. Concomitant medications

Ingredient	Ingredient code

Ibandronic acid*	480301BIJ 480302BIJ 480303BIJ 480304ATB 480330BIJ 487901ATB 523900ATB
Zoledronic acid*	420701BIJ 420702BIJ 420730BIJ 420731BIJ 420732BIJ
Risedronic acid*	442301ATB 442302ATB 500901ATB 442303ATB 511200ATB 518400ATB 442302ATE 442330ATB
Pamidronic acid*	207901ACS 207902BIJ 207903BIJ 207930BIJ
Alendronic acid*	228302ATB 228301ATB 228303ATB 468000ATE 481100ATR 500200ATB 481100ATB 228303ALQ 228305ATB 228306ALQ 228307ALQ
Etidronic acid*	147401ATB
Clodronic acid*	136101ACH 136102BIJ
Denosumab	629001BIJ

	629002BIJ
Teriparatide	487502BIJ 646301BIJ
Bazedoxifene [§]	617101ATB 674500ATB
Raloxifene [§]	358001ATB 358002ATB 659200ACH 659200ATB 698200ATB
Vitamin D	121401ACS 121402ACS 121601ACS 121602BIJ 121603BIJ 121604ACS 121604ATB 121630BIJ 316800BIJ 316900BIJ 317000BIJ 387900ACS 468000ATE 481100ATB 481100ATR 500200ATB 511200ATB 518400ATB 523900ATB 659200ACH 659200ATB 674500ATB 698200ATB
Calcium	357900ATB

*Following medications will be categorized as bisphosphonate: Ibandronic acid, Zoledronic acid, Risedronic acid, Pamidronic acid, Alendronic acid, Etidronic acid, Clodronic acid

[§]Following medications will be categorized as SERM: Bazedoxifene, Raloxifene

- On index date

- Type of administration (systemic HT (oral), systemic HT (transdermal), local HT (transvaginal)) (Table 4)

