7. RATIONALE AND BACKGROUND

Women at menopause may experience various changes due to ovarian failure and sex hormone deficiency¹. Globally, more than half of women aged 40-64 years experience menopausal symptoms such as hot flushes, night sweating, palpitation, sexual dysfunction, depression, insomnia and osteoporosis². These symptoms can disrupt various aspects of a person's life such as their ability to sleep, concentrate, maintain a good mood, feel energetic, carry out work, and engage in leisure or social activities³. Furthermore, the burden of medical treatment for menopausal symptoms is substantial and keeps increasing, highlighting the need for effective solutions to improve the quality of life for these population⁴.

Treatment guidelines recommend MHT for vasomotor symptoms and prevention of osteoporosis in women under 60 years of age or within 10 years of menopause and without contraindications⁵. However, since the Women's Health Initiative report and the Million Women Study were published, the use of MHT has declined rapidly^{6,7}. Also, many studies have reported a potential link between MHT and increased risk of cardiovascular disease, breast cancer, and endometrial hyperplasia⁸⁻¹⁰. Therefore, many menopausal individuals also seek treatment alternatives to MHT, including selective serotonin reuptake inhibitors, serotonin-norepinephrine reuptake inhibitors, gabapentin, and clonidine¹¹, although some of them have limited effectiveness and are also associated with specific adverse effects¹².

Recently, in light of the position statement on MHT, several menopause societies concur on the necessity of individualized MHT^{13,14}. Given that there is limited evidence on the latest MHT usage pattern using the most recent data in South Korea, we aim to estimate the prevalence of MHT among menopausal women and understand treatment patterns, adherence, and persistence among patients with menopausal hormone therapy in South Korea using the nationwide claims database from 2011 to 2020.

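### Table 5 leaves the six exclusion cancers out of the baseline Cancer row, but the exclusions are read before a different date, so some retained women with these cancers go uncounted

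*Combined protocol and SAP*

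**What the plan says.** **The Cancer row.** Table 5 in Section 9.3.3 gives the codes as "C00-C97 (except C22, C23, C24, C50, C54.1, C56"). The list containing it is headed "During 1-year prior to cohort entry date", and Section 9.2 agrees: "comorbidities, concomitant medications and proxies of health status will be assessed within 1 year prior to cohort entry date".

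**The exclusions.** Section 9.2 states: "The exclusion assessment window will be defined as the year before the index date". Section 9.2.2 repeats that anchor for each of its four criteria. The cancers it lists are breast (C50, D05), endometrial (C54.1), granulosa cell tumour (C56), hepatic (C22), gallbladder (C23) and extrahepatic bile duct (C24).

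**The two dates.** Section 9.2 defines them separately. Cohort entry is the day a menopausal symptom is first diagnosed, whereas "the index date will be defined as the date of the first prescription for MHT". The only limit on their spacing is the accrual period. The cohort consists of women "firstly diagnosed with menopausal symptoms and initiated MHT between January 1, 2012 and December 31, 2019".

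**Who is described.** Objective 2 (Section 8) covers patients with or without MHT, and the Abstract's data analysis text speaks of patients with menopausal symptoms. Sections 9.2, 9.3.3 and 9.7 speak of MHT initiators or patients with MHT.

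**The concern.** Leaving the exclusion cancers out of the Cancer row is harmless if the exclusions have already removed every woman with such a claim in the same year. The plan gives no reason for the exception, but the exact code match suggests that this was the assumption. It holds only when MHT starts on the day of cohort entry. Otherwise the exclusion year moves forward and uncovers the early part of the baseline year. Claims there neither exclude the woman nor count towards her Cancer row.

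What is at stake is the accuracy of one line in the Objective 2 baseline table. The line matters somewhat more than most, because Section 7 cites a potential link between MHT and "increased risk of cardiovascular disease, breast cancer, and endometrial hyperplasia". A reader will look to the baseline table to see how many cohort members had a recent history of breast cancer, and as defined the row cannot show any.

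**Working it through.** The plan states no figure for this point, so there is none to reproduce. The check has four steps.

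**1. Code sets.** The C-codes in Section 9.2.2 are C50, C54.1, C56, C22, C23 and C24. The codes excepted in Table 5 are C22, C23, C24, C50, C54.1 and C56. The sets are identical. D05 is also an exclusion code, but it lies outside C00-C97 and so would not be in the Cancer row in any case.

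**2. Window arithmetic.** Let E be cohort entry, I the index date and g = I − E, with g ≥ 0 assumed.

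- Baseline window: E − 365 up to E.
- Exclusion window: I − 365 up to I, that is, E + g − 365 up to E + g.
- Baseline days that the exclusion does not reach: min(g, 365).

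| Gap g (days) | Baseline days not reached | Share of the baseline year |
|---|---|---|
| 0 | 0 | 0% |
| 30 | 30 | 30/365 = 8% |
| 90 | 90 | 90/365 = 25% |
| 180 | 180 | 180/365 = 49% |
| 365 or more | 365 | 100% |

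The largest gap that the accrual period allows runs from 1 January 2012 to 31 December 2019: 8 × 365 + 2 leap days − 1 = 2,921 days. This is a calendar limit, not a typical value.

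**3. Worked cases.**

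- *Long gap.* C50 claims in June 2012; first N95.1 on 1 March 2013; first MHT on 1 June 2016; no C50 claim from June 2015 to May 2016. The exclusion year (1 June 2015 to 31 May 2016) is clear, so she is retained. Her baseline year (1 March 2012 to 28 February 2013) contains C50, and Table 5 discards it.
- *Short gap.* Entry on 1 March 2013 and MHT 90 days later, on 30 May 2013. The exclusion year begins on 30 May 2012. If her last C50 claim falls between 1 March and 29 May 2012, she is retained and not counted.

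**4. How many.** The documents give neither the distribution of g nor the frequency of these cancers, so no count is possible. A conditional share can be bounded under two assumptions that are not in the documents. The first is that a proportion q of women with one of the six codes in the baseline year have continuing claims that reach the exclusion window. The second is that for the others the last claim is uniform over the baseline year. The share retained but not counted is then (1 − q) × min(g, 365)/365.

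| Gap g (days) | q = 0 | q = 0.5 | q = 0.9 |
|---|---|---|---|
| 0 | 0% | 0% | 0% |
| 90 | 25% | 12% | 2% |
| 180 | 49% | 25% | 5% |
| 365 or more | 100% | 50% | 10% |

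The denominator is only women with one of the six codes in the baseline year, not the cohort.

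**Women without MHT.** Without a prescription there is no index date, so I − 365 is undefined and the exclusion cannot be evaluated as written. If these women are tabulated, the Table 5 exception still applies, and none of the six codes can appear in their Cancer row.

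**The case against.** The case for leaving the plan alone has real substance.

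- **Two anchors are not in themselves an error.** Reading exclusions before treatment start and characteristics before cohort entry is a defensible design. This stands. The fault lies in combining the two anchors with an exception that works only if they coincide.
- **Only a subset is affected.** A reader might infer that women with recent breast, endometrial or hepatobiliary cancer generally stay in the cohort. The documents do not support that. MHT must start after entry, and there must be no such claim in the whole year before MHT. Women with continuing claims are excluded as intended.
- **Table 5 prints its exception.** A reader might infer that these women are reported as cancer-free throughout. That goes too far: the row openly means cancer other than six codes, and CCI, read in the same year, may still score them. But the CCI code list is not given, and a composite score would not show which cancer was present.
- **Cardiovascular disease.** A reader might extend the point and say that the table understates coronary disease, stroke or VTE. It has no row for them, so it cannot understate them. It simply does not report them.
- **Women without MHT.** It is tempting to treat their misclassification as settled. It is not, because Sections 9.2, 9.3.3 and 9.7 restrict the description to MHT patients while Objective 2 and the Abstract are broader. Figures 1 and 2, which might clarify where the exclusions apply, are not shown in the text available.
- **Small consequence.** None of the outcomes in Section 9.3.2 uses this variable, and Section 9.7 plans no adjustment or formal comparison with it. This also stands.

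**Conclusion.** The point holds in a limited form. Table 5 drops exactly the cancers used as exclusions, but it does so in a window that the exclusions do not fully cover whenever MHT starts after cohort entry. The uncovered part is min(g, 365) days, which is the whole baseline year once the gap reaches 365 days. Retained women whose last claim falls there are missing from the Cancer row.

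The conclusion on windows follows from the stated definitions, taking a claim with the code as a diagnosis and assuming that MHT does not precede entry. The number affected is unknown, and the percentages under step 4 rest on assumptions. That the exception presumes prior removal is an inference from the code match. The part about women without MHT is conditional on their being described at all.

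The damage is confined to a descriptive baseline table. Prevalence, trends, switching, persistence and adherence do not use the variable. The change is still worth making, because it corrects a reported Objective 2 result at almost no cost.

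**What to change.** 1. In Table 5, remove the exception so that Cancer is C00-C97 in the year before cohort entry. Retained women with any of the six codes are then counted whatever the gap.
2. State whether women without MHT are described under Objective 2 and, if so, which reference date is used to apply the exclusions to them. Bring Sections 8, 9.2, 9.3.3 and 9.7 and the Abstract into line.
3. Optionally, add descriptive baseline rows for the exclusion conditions, in the same year before cohort entry, so that residual cases are visible. List D05 separately, since it lies outside C00-C97.

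The first change is a single table entry. The second is a sentence plus consistent wording. The third uses codes already listed in Section 9.2.2. None needs new data, and the first and third leave eligibility unchanged.
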